11.1. Appendix A Multiple Imputation (MI) Method

MI will adhere to the following steps:

Step 1: For non-monotone missing data, assuming the missing mechanism is missing at random (MAR), the MCMC method will be used with 100 iterations for imputation. The corresponding SAS option will be MCMC IMPUTE = MONOTONE. The number of imputed seeds will be set to 12345. The upper and lower bounds of the MDS-UPDRS Part III (Motor Examination) score will be [0, 132], with imputed scores rounded to the nearest integer. If applicable, covariates include whether stable levodopa-based anti-PD medication was received at screening (yes vs. no), baseline values (base), and scores at post-baseline visits (weeks 1, 4, 8, and 12 of treatment). The order in which these variables enter the procedure step follows the sequence listed above. The imputed data constitutes monotone missing data, and these 100 datasets will be utilized in Step 2. The reference program for the SAS PROC MI procedure is as follows:

```
PROC MI DATA=adeff NIMPUTE=100 OUT=mi_monotone SEED=12345
```

```
ROUND=.. 1 1 1 1
```

```
MIN =.. 0 0 0 0
```

```
MAX =.. 132 132 132 132;
```

```
MCMC IMPUTE=MONOTONE;
```

```
VAR pd base week1 week4 week8 week12;
```

```
RUN;
```

Step 2: For the monotone missing data imputed in Step 1, assuming the missing mechanism is MAR, use the MONOTONE REG method for imputation. The corresponding SAS PROC MI option is MONOTONE REG. The missing values at post-baseline visits will be imputed using the results from the immediately preceding visit. The seed number for imputation will be set to 23456. The reference program for the SAS PROC MI procedure is as follows:

```
PROC MI DATA=mi_monotone NIMPUTE=1 OUT=mi_complete SEED=23456
```

```
ROUND=.. 1 1 1 1
```

```
MIN =.. 0 0 0 0
```

```
MAX =.. 132 132 132 132;
```

```
MINMAXITER=1000;
```

```
BY _imputation_;
```

```
CLASS pd;
```

```
VAR pd base week1 week4 week8 week12;
```

```
MONOTONE REG(pd base week1 week4 week8 week12);
```

```
RUN;
```

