Step 3: The imputed complete data from Step 2 will be used for statistical analysis. First, the endpoint value will be calculated: the change from baseline in the Movement Disorder Society-Unified Parkinson's Disease Rating Scale (MDS-UPDRS) Part III (Motor Examination) score after 12 weeks of treatment (evaluation time point: ≥ 12 hours since the last dose of anti-PD medication). Then, recalculate the statistical measures for this endpoint (such as least squares mean differences and standard errors) to

obtain the statistical measures for 100 iterations. The reference program for the SAS PROC MIXED procedure is as follows:

```
PROC MIXED DATA=ANA_IMPUT4;  
  BY _imputation_;  
  CLASS pd trtpn avisitn usubjid;  
  MODEL chg = pd base trtpn avisitn avisitn*trtpn /ddfm=kenwardroger htype=3;  
  REPEATED avisitn/subject=usubjid type=&type:;  
  LSMEANS avisitn*trtpn/cl diff;  
  ODS OUTPUT lsmeans=mixedlsmeans1 diffs=diff1;  
run;
```

Step 4: Combine the 100 statistics using Rubin's method to obtain the pooled statistic, which serves as the final statistic for analysis. The reference program for the SAS PROC MIANALYZE procedure is as follows:

```
PROC MIANALYZE DATA=formianalyze;  
  MODELEFFECTS estimate;  
  STDERR stderr;  
RUN;
```

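### SAP Appendix A, Step 2 describes two different imputation models: its sentence names the preceding visit, while its program and Step 1 use the levodopa stratum, baseline and all earlier visits

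*SAP*

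**What the plan says.** SAP 11.1 (Appendix A) sets out the multiple imputation in four steps.

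- **Step 1** fills intermittent gaps by MCMC. Its text says that "covariates include whether stable levodopa-based anti-PD medication was received at screening (yes vs. no), baseline values (base), and scores at post-baseline visits" at Weeks 1, 4, 8 and 12, and the program lists the variables in that order.
- **Step 2** deals with the remaining monotone gaps: "For the monotone missing data imputed in Step 1, assuming the missing mechanism is MAR, use the MONOTONE REG method for imputation". The prose then adds: "The missing values at post-baseline visits will be imputed using the results from the immediately preceding visit". The program printed below it has "VAR pd base week1 week4 week8 week12" and a single list, "MONOTONE REG(pd base week1 week4 week8 week12".
- **Step 3** analyses each completed dataset with "MODEL chg = pd base trtpn avisitn avisitn*trtpn /ddfm=kenwardroger htype=3".
- **Step 4** pools the results by Rubin's rules.

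SAP 6.10.1 uses Appendix A in two places: Sensitivity Analysis 2 (treatment strategy) and Supplementary Analysis 2 (hypothetical strategy, where scores after the concomitant event are set to missing). The primary MMRM has no imputation. Protocol 11.4.3 leaves imputation detail to the SAP, so the protocol does not settle the matter.

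**The concern.** The Step 2 sentence and the Step 2 program describe different regressions. The sentence names one predictor, the score at the visit before. The program gives one list with no visit-specific effects, so each variable is regressed on all those ahead of it. Week 12 is then predicted from stratum, baseline and Weeks 1, 4 and 8.

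The SAP calls the code a reference program and does not rank it against the prose. As printed, the code also needs editing: a semicolon closes the PROC MI statement after the MAX list, which leaves MINMAXITER=1000 standing outside it. A programmer or validator who rebuilds the step could reasonably turn to the sentence. Two people could then deliver different results and both claim to have followed the SAP.

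The literal sentence is the weaker rule. It drops the stratum and baseline, both of which the Step 3 model conditions on. It also makes the missing-at-random assumption rest on a single earlier score. The primary MMRM tries an unstructured covariance first (SAP 6.10.1.1), so the plan does not otherwise assume that the last visit carries all the information.

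**Working it through.** The documents give no figure to reproduce here. SAP 4 states no statistical basis for the sample size and no SD, visit correlation or dropout rate. It does give about 50 subjects per group.

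**1. The two rules side by side (Week 12 missing, Week 8 observed)**

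| Source | Predictors of Week 12 |
|---|---|
| Step 2 sentence, taken literally | Week 8 |
| Step 2 program | stratum, baseline, Weeks 1, 4, 8 |
| Step 1 text | stratum, baseline and the post-baseline visits |
| Step 3 analysis model | stratum, baseline, treatment, visit, treatment by visit |

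Treatment group is in neither imputation rule.

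**2. Information lost, closed form**

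Assume equal correlation r between all visits and set the stratum aside. The residual variance of Week 12, as a fraction of its total variance, is:

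- given Week 8 alone: 1 − r²
- given baseline and Weeks 1, 4, 8: 1 − 4r²/(1 + 3r)

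| r | Week 8 alone | Full history | Ratio |
|---|---|---|---|
| 0.5 | 0.750 | 0.600 | 1.25 |
| 0.6 | 0.640 | 0.486 | 1.32 |
| 0.7 | 0.510 | 0.368 | 1.39 |
| 0.8 | 0.360 | 0.247 | 1.46 |
| 0.9 | 0.190 | 0.124 | 1.53 |

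Under AR(1), Week 12 given Week 8 does not depend on earlier scores, so the ratio is 1.00.

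**3. Effect on the pooled result, by simulation**

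Assumptions not in the documents:

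- SD 10; 60% on levodopa, with scores 4 points higher.
- True difference −4, building up evenly over the visits, or 0.
- Monotone dropout only, so Step 1 is not exercised.
- 300–400 trials per case, with 10–15 imputations (the plan has 100).
- ANCOVA at Week 12 standing in for the MMRM.

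Imputed scores are rounded and bounded at 0–132, as in Appendix A. The first two methods omit treatment, as both the sentence and the program do. The last column adds it. In the baseline-by-arm case, one SD of baseline moves the log-odds of dropout by 1, upwards on active drug and downwards on placebo.

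| Correlation | Dropout | True diff. | Missing at Week 12 | SE, preceding visit | SE, full history | SE ratio | Estimate, preceding visit | Estimate, full history | Estimate, full history + treatment |
|---|---|---|---|---|---|---|---|---|---|
| equal 0.6 | completely random | −4 | 10% | 1.80 | 1.70 | 1.06 | −3.61 | −3.59 | −3.91 |
| equal 0.6 | completely random | −4 | 19% | 1.96 | 1.79 | 1.09 | −3.39 | −3.35 | −4.01 |
| equal 0.6 | recent change | −4 | 22% | 2.02 | 1.81 | 1.12 | −3.32 | −3.23 | −4.04 |
| equal 0.8 | completely random | −4 | 10% | 1.40 | 1.27 | 1.10 | −3.73 | −3.68 | −4.00 |
| equal 0.8 | completely random | −4 | 18% | 1.55 | 1.34 | 1.16 | −3.48 | −3.43 | −4.05 |
| equal 0.8 | baseline, by arm | −4 | 24% | 1.68 | 1.40 | 1.20 | −4.31 | −3.00 | −3.93 |
| equal 0.8 | baseline, by arm | 0 | 24% | 1.66 | 1.37 | 1.21 | −1.16 | +0.06 | +0.07 |
| AR(1) 0.8 | completely random | −4 | 18% | 1.98 | 1.99 | 0.99 | −3.48 | −3.48 | −4.04 |
| AR(1) 0.8 | baseline, by arm | −4 | 24% | 2.08 | 2.09 | 1.00 | −3.15 | −3.09 | −3.94 |

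For scale, the Monte Carlo error of the −1.16 is about 1.23/√300 = 0.07.

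**What the table shows**

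- The preceding-visit rule inflates the pooled SE by 6–21% under equal correlation and not at all under AR(1).
- The loss is mainly in the reported SE and interval width. The estimate's actual spread changes little, for example 1.18 against 1.11 at equal 0.8 with 18% missing.
- The two rules give nearly the same estimate unless dropout depends on baseline differently by arm and correlations do not decay.
- Omitting treatment pulls the estimate towards zero under either rule when dropout is completely random or follows recent change. Adding treatment removes this.

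**The case against.** The best defence is that the sentence is a loose description of visit-by-visit monotone imputation. It does not contain the word only and does not exclude baseline, stratum or earlier visits. The sentence before it prescribes the monotone regression method, and the program below it and Step 1 agree on the fuller set. A strict preceding-visit rule would need visit-specific regression statements that the SAP never shows. This stands in part. The documents do not establish that the SAP restricts the predictors to one visit, and a reader who infers that goes too far. What remains is that the sentence names one predictor, conflicts with its own program, and is not resolved anywhere.

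A reader might also infer a general bias of about one point. The documents do not support that. The figure comes from a deliberately severe dropout pattern with assumed equal correlations. With a true difference of −4 in that same pattern, shrinkage from omitting treatment partly offsets the preceding-visit error, so the literal rule (−4.31) lies nearer the truth than the printed program (−3.00). That is accidental cancellation and does not recommend the literal rule. It does show that copying the program's predictor list into the prose would leave a larger gap untouched.

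Finally, it can be said that little depends on this. That is largely right: P-values are nominal (SAP 6.1), and neither the primary MMRM nor Sensitivity Analysis 1 nor Supplementary Analysis 1 uses Appendix A.

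**Conclusion.** The contradiction in Step 2 is real and can be seen by reading. If the sentence were followed literally, Sensitivity Analysis 2 and Supplementary Analysis 2 would use a poorer imputation model that leaves out covariates of the Step 3 model. The cost is a pooled SE roughly 6–21% larger under assumed equal visit correlations of 0.6–0.8 with 10–24% missing, and none under AR(1). Extra bias in the treatment difference needs dropout that depends on baseline or early scores differently by arm.

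It would be tempting to conclude that these analyses could not be interpreted as robustness checks. A change in SE of this order does not support that. The point is that a departure from the primary result might partly reflect an unsettled imputation rule. Severity is minor to moderate.

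**What to change.** Replace the Step 2 sentence with: *Missing scores at each post-baseline visit will be imputed by regression on treatment group, levodopa stratum, baseline and all earlier post-baseline visits.*

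Then match the programs to it:

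- Add treatment group to the Step 1 and Step 2 variable lists, because it is the effect that Step 3 estimates. The three arms can enter Step 1, which has no CLASS statement, as two indicator variables.
- Extend the ROUND, MIN and MAX lists, which are positional, to cover the added variables.
- Remove the semicolon before MINMAXITER in Step 2.

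The cost is one sentence and a few lines of code, with no new data. It should be settled before the SAP is signed and the database locked (Protocol 5.3.2.2), so that the rule is not chosen with results in view.
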